## **Study Protocol**

Prior to any involvement in the study, a study investigator read the VA-approved consent forms in full to the potential subject. Having been read the consent forms and provided with an explanation of the experimental tasks, the potential subject was provided an opportunity to ask questions. Following this, if they agreed to participate, they signed a consent form. Each prosthesis user subject was assessed using their clinically prescribed prosthesis (i.e., socket, suspension system, pylon, and foot).

Following demographic information data collection, retro-reflective markers were attached to the subject with hypoallergenic adhesive tape to anatomical landmarks as specified in the modified Helen Hayes full-body marker set with additional markers placed on the right and left acromion processes, lateral epicondyle of the humerus, and between the styloid process of the radius and ulna. Position of the markers on the prosthetic limb approximated matched those on the contralateral side. Additionally, surface electrodes for measurement of electromyography (EMG), or muscle activity, were placed and secured over the following muscles: tibialis anterior of the sound limb (or both limbs in case of control subjects), medial gastrocnemius of the sound limb (or both limbs in case of control subjects), rectus femoris of both limbs, medial hamstring of both limbs, and gluteus medius of both limbs.

Subjects were requested to perform three biomechanical tasks (randomized prior to their visit) at the JBVAMC Motion Analysis Research Laboratory:

1. Quiet standing with comfortable stance width and eyes open,
2. Quiet standing with comfortable stance width and blindfolded, and
3. Walking at two self-selected speeds (normal and fast) across a level walkway.

**Walking Data Collection**—During the walking trials, subjects walked at a comfortable, normal, self-selected speed down the center of a 10 meter level walkway. The subjects were requested to walk back and forth along this walkway as many times as necessary to produce 10 clean foot strikes (i.e., each foot within the boundaries of at least one force plate). After walking at their normal speed, subjects were then requested to perform the same walking task while at their self-selected “fast” speed, defined as “a speed as if you were hurrying for a bus.”

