**Quiet Standing Data Collection**—During standing trials, subjects stood quietly with a comfortable stance width, as determined during an initial practice trial, with each foot on one adjacent force plate. This allowed recording of the plantar center of pressure (CoP) under both limbs by each force plate. The stance position was marked by tracing the feet on the floor. The subject was asked to replicate this stance position for all subsequent trials. During the eyes open condition, subjects were instructed to focus on a visual target mounted at eye level on the wall 5 meters in front. During the eyes closed standing condition, a blindfold was worn by the subjects to remove all visual cues. For each task,

data were recorded for 30 seconds. Three trials of both the eyes open and closed conditions will be performed.

Self-selected walking speeds and stance width were tested to better reflect real-life conditions and facilitate the subjects' comfort during testing. Subjects were provided with seated rest between the three tasks to successfully carry out all walking and standing trials.

**Prospective fall data collection**—Prospective data on falls were collected monthly over a 12 month period following their second visit using a validated, rigorous 'falls calendar' approach. Subjects were provided with twelve (prepaid postage) postcards that consist of a falls calendar. Subjects were instructed on how to use the postcards following established guidelines and post them to the primary investigator directly at the JBVAMC Motion Analysis Research Laboratory every month following the data collection session. This postcard was mailed with no return address to ensure confidentiality. The identity of each subject was determined by their unique subject code, which was written on the postcards before distribution and known only to the research team. Following receipt of a postcard that reported one or more falls during the month data collection period, the subject was contacted via telephone or email and asked standardized questions regarding the location and activity engaged in preceding the fall, what they felt caused the fall, and if injuries were sustained. Subjects were contacted via post, telephone or email if a postcard is not returned within 7 days after each month period and/or to query unclear entries.

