## Statistical Analysis Plan

The main effect of amputation and limb side on kinematic variables will be assessed using a linear mixed model analysis for each walking speed separately. The main effect of amputation and limb side on standing balance variables will be assessed using a linear mixed model analysis for each vision condition separately. The main effect of amputation and walking speed on EMG variables will be assessed using a linear mixed model analysis for each muscle group separately. The total number of falls for each group will be calculated for each group.

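### The only planned falls summary is a bare total per group; reporting subjects, reported months, a rate and faller counts beside it would be a minor, cheap improvement

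*Combined protocol and SAP*

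**What the plan says.** The Statistical Analysis Plan has one sentence on falls: "The total number of falls for each group will be calculated for each group". The kinematic, standing balance and EMG variables each get a model; for balance, for example, "The main effect of amputation and limb side on standing balance variables will be assessed using a linear mixed model analysis".

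The Study Protocol, in its paragraph on prospective fall data, collects much more than a sum needs:

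- **Duration:** "Prospective data on falls were collected monthly over a 12 month period following their second visit".
- **Instrument:** "Subjects were provided with twelve (prepaid postage) postcards that consist of a falls calendar".
- **Linkage to the subject:** "The identity of each subject was determined by their unique subject code, which was written on the postcards before distribution".
- **Late cards:** "Subjects were contacted via post, telephone or email if a postcard is not returned within 7 days after each month period". Unclear entries are queried in the same way.

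There are at least two groups. The protocol describes prosthesis users, and its electrode placement text refers to controls: "tibialis anterior of the sound limb (or both limbs in case of control subjects".

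The available text gives no group sizes, expected fall rate or expected return rate. For falls it gives no denominator, no count of subjects who fell, no rule for a month that stays missing after contact, and no interval.

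**The concern.** A total is the product of three things: how often people fall, how many people are in the group, and how many months they report. Two totals side by side can differ for any of these reasons, and the plan does not say that the other two will be shown.

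Three further features are lost in the sum:

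- A month with no report after contact adds nothing, so in effect it counts as a month without falls.
- The same total can come from many people who fell once or from a few who fell repeatedly.
- No measure of precision accompanies it.

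What is at stake is whether a year of prospective follow-up can be interpreted. This total is the only falls result planned.

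**Working it through.** The plan states no falls figure, so there is nothing to reproduce. From the documents come the 12 months, the 12 cards per subject and the contact step. Every other input below is an assumption chosen to show a range.

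**1. Group size and months reported.** Rate = total / (subjects × 1 year × share of months reported). Take a total of 12 falls.

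| Subjects | All months reported | 25% of months missing |
|---|---|---|
| 10 | 12/10 = 1.20 per person-year | 12/7.5 = 1.60 |
| 15 | 12/15 = 0.80 | 12/11.25 = 1.07 |
| 20 | 12/20 = 0.60 | 12/15 = 0.80 |

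One total is therefore compatible with rates from 0.60 to 1.60. Between groups with equal rates, 20 v 30 subjects give totals 30/20 = 1.5-fold apart; with equal sizes this effect vanishes. Return of 90% v 95% changes the ratio of totals only to 0.90/0.95 = 0.95, while 75% v 95% changes it to 0.75/0.95 = 0.79.

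**2. How many subjects need a missing-month rule.** With independent misses, P(all 12 reported) = p^12. With misses clustered within subjects (beta-binomial, intraclass correlation ρ), put s = (1−ρ)/ρ and a = p·s; then P = ∏(a+i)/(s+i) for i = 0 to 11.

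| Monthly return p | Independent | ρ = 0.2 | ρ = 0.5 |
|---|---|---|---|
| 90% | 28% | 54% | 73% |
| 95% | 54% | 74% | 85% |

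Even in the most favourable cell, about 15% of subjects lack at least one month.

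**3. Who fell.** With a mean of 1 fall per year, and so the same expected total, the share with at least one fall is 1 − exp(−1) = 63% with no overdispersion. It is 1 − (1+k)^(−1/k) at negative binomial dispersion k: 50% at k = 1 and 42% at k = 2. Missing months also affect this share. With 25% missing at random and k = 1, observed fallers are 1 − 1/(1 + 0.75) = 43% instead of 50%. Faller percentages therefore need a stated denominator.

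**4. Precision.** Take 20 falls in 20 subjects followed for a year, a rate of 1.0. The standard error of the log rate is √(1/20 + k/20), and t on 19 df is 2.093.

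- k = 0, normal quantile: exp(±1.96 × 0.224) = 0.65 to 1.55.
- k = 1, normal quantile: exp(±1.96 × 0.316) = 0.54 to 1.86.
- k = 1, t quantile, as in the suggested interval: exp(±2.093 × 0.316) = 0.52 to 1.94.

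In gamma-Poisson simulation (40,000 replicates, 10 or 20 subjects, 1 to 2 falls per year, k from 0 to 2), a log-scale interval with subject-level robust variance and t on n−1 df covered about 92% to 97%. At 20 subjects, an exact Poisson interval, which treats falls as independent, fell to 64% at 2 falls per year and k = 2.

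**5. Missing months related to falling.** Suppose 80% of months with a fall and 95% of other months are reported, at 1 fall per year. P(fall in a month) = 1 − exp(−1/12) = 0.080. The total is 0.80 of the truth. The rate on reported time is 0.80/(0.080 × 0.80 + 0.920 × 0.95) = 0.80/0.938 = 0.85 of the truth. Person-time reduces this bias but does not remove it.

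**The case against.** The strongest reply is that nothing in the plan depends on this number. There is no falls hypothesis, test or stated comparison. The total is a true count of reported falls, and the plan does not call it a rate or a risk. That stands, and it is why the point is minor.

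Second, every subject has the same intended 12 months, and late cards are chased. If group sizes are reported and return is nearly complete, total divided by subjects is close to a rate. Part of the document was not available for review, so the absence of group sizes from the rest is weak evidence that the plan lacks them. This largely answers the denominator point. It does not recover the number of fallers, the repeat fallers, the months missing or the precision. The contact step governs how data are retrieved, not what the analysis does when contact fails.

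Third, non-return plausibly clusters within subjects, so the independence figures overstate how many people have a gap. That is correct, which is why both cases are shown.

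A reader might infer that the planned totals will give a false answer on whether prosthesis users fall more than controls, or that a rate-ratio model is required. The documents support neither. They plan no such inference, and they give no group sizes or return rates from which a distortion could be shown.

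**Conclusion.** The point holds as a minor reporting improvement. Followed as written, the plan reduces subject-by-month falls data to a sum that mixes rate, group size and reported time, treats unreported months as contributing no falls, and hides repeat falling. The textual gap is certain; its consequence is not.

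The effect on the totals could be nil (equal groups, full return), small (ratio 0.95 at 90% v 95% return), or as large as the 1.5-fold example, which rests on assumed sizes of 20 and 30. That example should not be read as an expected distortion. The need for a missing-month rule is better supported: at 90% to 95% return, between 15% and 72% of subjects lack a month over the clustering assumptions shown (100% minus 85% and 28%).

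**What to change.** Keep the total and add to the Statistical Analysis Plan, for each group:

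- the number of subjects, person-months reported, and months still missing after contact;
- falls per person-year of reported time, with a 95% confidence interval that allows for repeat falls within a subject, for example subject-level robust variance on the log scale with t on n−1 df;
- the number and percent of subjects with at least one and at least two falls, given first among all subjects with at least one reported month and again among those with all 12.

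State that months without a report after contact are left out of the person-months. List subjects with no reported month and exclude them from both the rate and the faller percentages. If a group has no falls, report zero with its person-months, and label any Poisson upper limit as assuming independent falls. No between-group model is needed unless the groups are to be formally compared.

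**Cost:** a few table rows and no new data, because cards already carry a subject code and refer to a month. Intervals will be wide in small groups, as the 0.52 to 1.94 example shows. Bias is reduced but not removed if missing months are related to falling.
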